1.10 Disulfiram and Copper Administration

Although the MTD of DSF in combination with adjuvant temozolomide was established at 500 mg once per day, continuous administration of this dose over time was associated with reversible delirium or neuropathy that prompted discontinuation of therapy in some patients. Furthermore, the pharmacodynamics study showed that 500 mg DSF per day (without concurrent Cu) produced limited proteasome inhibition on peripheral blood cells, one of the presumed mechanisms against glioblastoma cells (Huang et al 2016). Given that Cu has been shown to be essential for DSF's anti-cancer effects, co-administration of Cu with DSF may be necessary to maximize its efficacy (Hothi, et al. 2012; Lun, et al. 2016). A previous phase I study for patients with advanced liver metastasis showed that 6 mg of elemental Cu in the form of copper gluconate is well tolerated when given with 250 mg of DSF daily. In this study, Cu was given in the morning half hour before breakfast, and DSF was given with the evening meals to avoid gastro-intestinal irritation from complexation of DSF and Cu in the stomach (Grossmann, et al. 2011).

A recent double-blinded, randomized phase II study compared chemotherapy with and without DSF for metastatic non-small cell lung cancer. Patients who received concurrent DSF had significantly better PFS and OS than those who received chemotherapy alone (5.9 vs. 4.9 months, and 10.0 vs. 7.1 months, respectively) (Nechushtan, et al. 2015). In that study, DSF was given at 40 mg TID. In contrast to the Huang phase I study, Nechushtan *et al.* did not report any significant neurological toxicity except fatigue. This study suggests that lower DSF daily dosing may be more effective than higher dose. Given the results of this study and our ANII patient derived primary culture data which suggests that lower DSF dose may be more effective this study will limited DSF total daily dose to 250 mg split into two 125 mg doses given on a BID schedule.

1.11 Study Rationale

Patients with unmethylated glioblastoma respond poorly to current standard treatment and have a poor prognosis.

Although standard post resection radiation therapy may provide a survival benefit of approximately two months, delayed radiation at or after 8 weeks has been shown to not increase overall survival. This study proposes standard of care treatment with 6 – 6 1/2 weeks of radiation with concurrent temozolomide at 75mgs / m² along with DSF – Cu followed by adjuvant temozolomide at 150mgs / m² for 6 -12 cycles in patients with previously untreated, (aside from surgical resection), unmethylated glioblastoma.

Preclinical studies have identified DSF-Cu as having promising activity in glioblastoma cells and can potentially sensitize temozolomide-resistant cells to temozolomide.

A recent phase I study has demonstrated the feasibility and safety of combining DSF with adjuvant temozolomide in newly diagnosed glioblastoma patients after chemoradiotherapy (Huang, et al. 2016). This clinical trial will evaluate whether the addition of DSF-Cu to temozolomide in patients expected to be temozolomide-resistant can induce anti-tumor responses and validate the potential of DSF-Cu to sensitize glioblastoma to temozolomide.

2.0 STUDY OBJECTIVES

2.1 Primary Objective

1. To determine evidence of an antitumor effect in patients with unmethylated glioblastoma treated concurrently with DSF-Cu and concurrent radiation and temozolomide. To determine *6 month PFS and 12 month OS of patients with unmethylated glioblastoma treated with DSF-Cu in combination with concurrent radiation and temozolomide.*

2.2 Secondary Objectives

2. To evaluate the safety and tolerability of DSF-Cu administered BID when given concurrently with temozolomide.
3. To determine the impact of DSF + Cu on the quality of life (QOL) for patients with newly diagnosed GBM undergoing standard concurrent radiation and temozolomide treatment followed by adjuvant temozolomide.

3.0 PATIENT SELECTION

Approximately 14-40 patients will be enrolled – depending on the preliminary subset analysis data (when accrual of 14 patients is reached) the study may conclude when 14-20 patient mark is reached.

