3.1 Inclusion Criteria

1. Age 18 or older
2. Diagnosis of histologically confirmed glioblastoma (WHO grade IV). Subjects with an original histologic diagnosis of low grade glioma or anaplastic glioma (WHO

- grade II or III) are eligible if a subsequent histological diagnosis of glioblastoma is made
3. Patients whose tumor is determined to be unmethylated
 4. Patients with incomplete resection as determined by residual, measurable gadolinium or contrast-enhancing lesion or lesions
 5. Recent resection of glioblastoma. Patients who have only had a tumor biopsy and who are considered unresectable are eligible (but based on the study accrual this subset of patients with unresectable tumor may be considered for separate analysis)
 6. ECOG PS of ≤ 2 (see appendix A)
 7. Willing to remain abstinent from consuming alcohol while on DSF
 8. No prior radiation or chemotherapy
 9. Meets the following laboratory criteria:
 - a. Absolute neutrophil count $\geq 1,500/\text{mcL}$
 - b. Platelets $\geq 100,000/\text{mcL}$
 - c. Hemoglobin $> 10.0 \text{ g/dL}$ (transfusion and/or ESA allowed)
 - d. Total bilirubin and alkaline phosphatase $\leq 2x$ institutional upper limit of normal (ULN)
 - e. Aspartate aminotransferase (AST) and alanine aminotransferase (ALT) $< 3 \times$ ULN
 - f. Blood urea nitrogen (BUN) and creatinine $< 1.5 \times$ ULN
 10. Able to take oral medication
 11. Able to understand and willing to sign an institutional review board (IRB)-approved written informed consent document (legally authorized representative permitted)
 12. MRI with and without contrast prior to enrollment.

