10.0 STATISTICAL CONSIDERATIONS

10.1 Definition of Primary Endpoints and Analytical Plan

The co-primary endpoints will be ORR and PFS6. ORR will be defined as the percentage of patients with CR or PR according to the RANO criteria as described in Section 6.0. PFS6 will be defined as proportion of patients that are free from progressive disease (PD) as per RANO criteria or death at 6 months from the date of the first dose of DSF-Cu. PFS6 and median PFS will be estimated using the Kaplan-Meier product-limit method. For unmethylated glioblastoma receiving temozolomide without DSF-Cu, an ORR of less than 10% and PFS6 of less than 20% (Quinn, et al. 2009).

To justify future use of or drug development of DSF-Cu for glioblastoma, we hypothesized that the addition of DSF-Cu to temozolomide would improve ORR to 20% or increase PFS6 to 30%. The sample size is calculated based on the above hypotheses with one-sided exact test at an approximate α level of 0.10 and 80% statistical power. At these type I and II error rates, 14 -20 patients will detect a proportion of patients who have ORR significantly higher than 5% or PFS6 significantly higher than 10%. Of note, previous phase II study testing addition of O⁶-benzylguanine (a MGMT inhibitor) to temozolomide for temozolomide-resistant glioblastoma used similar hypothesis and observed a disappointing ORR of 3% and PFS6 of 9% (Quinn, et al. 2009). This negative phase II study has detailed information on ORR, PFS, and OS as well as associated estimated 95% CIs and will serve as a historical comparison for this study.

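### The look at 14 patients has no endpoint, direction or boundary, and Sections 3.0 and 10.1 give different sizes (14-40 and 14-20), so the design's alpha and power cannot be derived; as a final fixed sample, 14 misses 80% power on each endpoint

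*Combined protocol and SAP*

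**What the plan says.** Section 3.0 states "Approximately 14-40 patients will be enrolled" and continues that, "depending on the preliminary subset analysis data (when accrual of 14 patients is reached) the study may conclude when 14-20 patient mark is reached". It does not say which patients form the subset, which endpoint is examined, what result ends or continues the study, or whether an early end would mean success or futility.

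Section 10.1 holds the only sample-size statement. The co-primary endpoints are ORR and PFS6. The hypothesis is that DSF-Cu would "improve ORR to 20% or increase PFS6 to 30" percent. The test is one-sided and exact, at an approximate alpha "level of 0.10 and 80% statistical power". It concludes that "14 -20 patients will detect a proportion of patients" with "ORR significantly higher than 5% or PFS6 significantly higher than 10" percent. No critical values, interim look or calculation beyond 20 patients is given. Section 10.1 also gives background rates without DSF-Cu of under 10% for ORR and under 20% for PFS6, which differ from the 5% and 10% used for sizing. Section 10.2 adds nothing on this point.

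Section 3.1 uses the same word for biopsy-only patients: "this subset of patients with unresectable tumor may be considered for separate analysis".

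**The concern.** A trial whose final size depends on its own data has error rates set by the rule that links the two. Without that rule, a reader cannot attach an alpha to a positive result or a power to a negative one. Writing the rule after the data at 14 have been seen would not repair this. Section 10.1 intends the result to justify further use or development of DSF-Cu, so its stated error rates matter.

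The look itself can be read in more than one way. The subset may be the first 14 patients or the biopsy-only group. Accrual of 14 may fix the date of the look or only identify who is analysed. If it fixes the date, the most recent patients cannot yet have a PFS6 status, which is defined "at 6 months from the date of the first dose of DSF-Cu". They also would not have a response scan: Section 4.3 schedules MRI every 8 weeks, and the Section 9.0 calendar places it at the end of even-numbered cycles.

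**Working it through.** **Inputs.** From Section 10.1: PFS6 null 10%, alternative 30%; ORR null 5%, alternative 20%; one-sided exact test, alpha about 0.10, power 80%, n = 14-20. From Section 3.0: n = 14-40, look at 14. Assumption: every patient's response and 6-month status is known, so each endpoint is a simple count.

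**Formula.** P(X ≥ r | n, p) = Σ (k = r to n) C(n,k) p^k (1−p)^(n−k). The critical value r is the smallest with P(X ≥ r | n, p0) ≤ 0.10; power is P(X ≥ r | n, p1).

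**Step 1. The plan's 14-20.** The smallest n with exact alpha ≤ 0.10 and power ≥ 80% is 18 for PFS6 and 21 for ORR. The upper end of the range is therefore close, but the lower end is not reproduced. A normal approximation, n = [(z0.90 √(p0(1−p0)) + z0.80 √(p1(1−p1))) / (p1−p0)]², gives 14.8 for PFS6 and 16.9 for ORR, that is 15 and 17. Those lie inside the range, but the plan specifies an exact test, and 14 is below both.

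**Step 2. Fixed n = 14.**
- PFS6, p = 0.10: P(0 to 3) = 0.2288 + 0.3559 + 0.2570 + 0.1142 = 0.9559, so ≥4/14 has alpha 0.044. At p = 0.30: 0.0068 + 0.0407 + 0.1134 + 0.1943 = 0.3552, so power is 0.645.
- ORR, p = 0.05: P(0 to 2) = 0.4877 + 0.3593 + 0.1229 = 0.9699, so ≥3/14 has alpha 0.030. At p = 0.20: 0.0440 + 0.1539 + 0.2501 = 0.4480, so power is 0.552.
- One cutoff lower: PFS6 ≥3/14 has alpha 0.158 and power 0.839; ORR ≥2/14 has alpha 0.153 and power 0.802.

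**Step 3. Each n from 14 to 21, alpha ≤ 0.10.**

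| n | PFS6 r | alpha | power | ORR r | alpha | power |
|---|---|---|---|---|---|---|
| 14 | 4 | 0.044 | 0.645 | 3 | 0.030 | 0.552 |
| 15 | 4 | 0.056 | 0.703 | 3 | 0.036 | 0.602 |
| 16 | 4 | 0.068 | 0.754 | 3 | 0.043 | 0.648 |
| 17 | 4 | 0.083 | 0.798 | 3 | 0.050 | 0.690 |
| 18 | 4 | 0.098 | 0.835 | 3 | 0.058 | 0.729 |
| 19 | 5 | 0.035 | 0.718 | 3 | 0.067 | 0.763 |
| 20 | 5 | 0.043 | 0.762 | 3 | 0.076 | 0.794 |
| 21 | 5 | 0.052 | 0.802 | 3 | 0.085 | 0.821 |

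Within 14-20, PFS6 reaches 80% only at 18 and ORR never does. Both do at 21.

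**Step 4. Success on either endpoint at n = 14.**
- Both alternatives true, endpoints independent: 1 − (1 − 0.645)(1 − 0.552) = 0.841.
- Successes fully overlapping: 0.645.
- Only PFS6 improves, independent: 1 − (1 − 0.6448)(1 − 0.0301) = 0.656 (unrounded inputs).
- Only ORR improves, independent: 1 − (1 − 0.552)(1 − 0.044) = 0.572.

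**Step 5. How PFS6 error rates move with the rule.** Each line adds the chance of crossing at 14 to the chance of crossing first at the later look.
- Success tested at nominal 0.10 at 14 and 20 (≥4, then ≥5): 0.0441 + 0.0176 = 0.062.
- At 14 and 40 (≥4, then ≥7): 0.0441 + 0.0752 = 0.119.
- ≥4/14, then ≥8/40: alpha 0.072, power 0.6448 + 0.3073 = 0.952.
- Futility-only look, with the final test at its fixed-sample cutoff: stopping can only remove rejections, so there is no inflation.

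**The case against.** **The power at 14 depends on how 14 is used.** The figures 0.645 and 0.552 belong to a fixed test on 14 patients. If 14 is an interim look, power belongs to the whole design: the ≥4/14 then ≥8/40 rule can end at 14 with success and has PFS6 power 0.952. A reader might infer that any trial ending at 14 has 55-65% power. The documents do not support that, because they do not say whether 14 is a final sample or a look. This part of the objection stands, and the shortfall is limited to 14 as the final fixed sample.

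**Section 10.1 says or.** On an either-endpoint reading, power at 14 can be 0.841. But Section 10.1 states no such decision rule. The figure needs both alternatives true and independent endpoints; the other assumptions tried give 0.57-0.66. That reading also spends alpha: with independent endpoints, the joint alpha is 1 − (1 − 0.098)(1 − 0.058) = 0.151 at n = 18 and 1 − (1 − 0.043)(1 − 0.076) = 0.116 at n = 20 from these rounded inputs.

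**Alpha is only approximate.** That wording might cover a little over 0.10, but hardly 0.15-0.16.

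**Inflated type I error.** A reader might infer that the plan inflates alpha. That needs success tested at 14 and again out to 40, which no section describes. For PFS6, looks at 14 and 20 stay at 0.062. The defect is that the rule is missing, not that a bad rule is written.

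**Larger n is not short of power.** This is true. A fixed 40 has power 0.976 for PFS6 (≥7, alpha 0.0995) and 0.924 for ORR (≥5, alpha 0.048). The missing calculation for 21-40 is a gap in specification, not a power deficit.

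**Conclusion.** The point holds in a limited form. The maximum sample size differs between Sections 3.0 and 10.1, and the look that decides when the study ends has no endpoint, direction or boundary. The final n, alpha and power of the design cannot be derived from the documents. Separately, the claim of 80% power across 14-20 patients fails per endpoint at the lower end: a fixed final 14 falls short by about 16 percentage points for PFS6 (80 − 64.5) and 25 for ORR (80 − 55.2). These figures rest on the 5%/10% nulls and 20%/30% alternatives in Section 10.1, exact alpha no greater than 0.10, and complete data.

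The identity of the subset and the date of the look are ambiguous. Section 3.1 does not link the biopsy-only group to stopping, and immature data are a problem only if accrual of the 14th patient fixes the date. The rule should be settled before the data at 14 are examined.

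**What to change.** In Sections 3.0 and 10.1:

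1. State one maximum n in both places.
2. Say who the subset is.
3. Base the look on 14 patients who have each reached 6 months, progression or death, and say whether accrual pauses meanwhile.
4. Pre-specify the look's endpoint, direction and numeric boundary.
5. Replace the claim of 80% power for 14-20 patients with the exact alpha and power of that design, including the joint alpha if success on either endpoint counts.

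**Illustration, PFS6 at the 10% null.** Stop at ≤1/14; success at ≥4/18. Rejection probability is Σ (k = 2 to 14) b(k; 14, p) P(Y ≥ 4 − k | 4, p), where b is the binomial probability: alpha 0.097 (0.098 if the stop is ignored), power 0.832 at 30%. Two caveats go with it:

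- Section 10.1's background PFS6 is under 20%, not 10%. At a true PFS6 of 20% this rule succeeds with probability 0.495. The null rates must be reconciled before any boundary is adopted.
- Testing PFS6 alone makes ORR descriptive. Keeping both endpoints with an either-endpoint rule needs a larger maximum. For example, with 27 patients, success at PFS6 ≥6 or ORR ≥4 has total alpha at most 0.047 + 0.044 = 0.091 under any correlation. Power is at least 0.849 if PFS6 is 30% and at least 0.807 if ORR is 20%, when the look at 14 stops only with ≤1 patient progression-free at 6 months and no CR or PR. That maximum is inside the 40 in Section 3.0 but above the 20 in Section 10.1. It depends on the nulls in the same way: at a true ORR of 10%, ≥4/27 occurs with probability 0.282.

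**Cost.** The two sections must be reworded and a sample size chosen: 18 with ORR no longer tested, or about 27 with both endpoints. The look waits for 6-month data. Without an accrual pause, a maximum of 18 could leave little to save by stopping at 14. A futility-only look gives up early stopping for success; a success boundary is equally acceptable if its total alpha is shown.

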3.1 Inclusion Criteria

1. Age 18 or older
2. Diagnosis of histologically confirmed glioblastoma (WHO grade IV). Subjects with an original histologic diagnosis of low grade glioma or anaplastic glioma (WHO

- grade II or III) are eligible if a subsequent histological diagnosis of glioblastoma is made
3. Patients whose tumor is determined to be unmethylated
 4. Patients with incomplete resection as determined by residual, measurable gadolinium or contrast-enhancing lesion or lesions
 5. Recent resection of glioblastoma. Patients who have only had a tumor biopsy and who are considered unresectable are eligible (but based on the study accrual this subset of patients with unresectable tumor may be considered for separate analysis)
 6. ECOG PS of ≤ 2 (see appendix A)
 7. Willing to remain abstinent from consuming alcohol while on DSF
 8. No prior radiation or chemotherapy
 9. Meets the following laboratory criteria:
 - a. Absolute neutrophil count $\geq 1,500/\text{mcL}$
 - b. Platelets $\geq 100,000/\text{mcL}$
 - c. Hemoglobin $> 10.0 \text{ g/dL}$ (transfusion and/or ESA allowed)
 - d. Total bilirubin and alkaline phosphatase $\leq 2x$ institutional upper limit of normal (ULN)
 - e. Aspartate aminotransferase (AST) and alanine aminotransferase (ALT) $< 3 \times$ ULN
 - f. Blood urea nitrogen (BUN) and creatinine $< 1.5 \times$ ULN
 10. Able to take oral medication
 11. Able to understand and willing to sign an institutional review board (IRB)-approved written informed consent document (legally authorized representative permitted)
 12. MRI with and without contrast prior to enrollment.

3.2 Exclusion Criteria

1. Radiographic evidence of leptomeningeal dissemination, extensive intraparenchymal dissemination, infratentorial tumor, or metastatic disease to sites remote from the supratentorial brain
2. Enrolled in another clinical trial testing a novel therapy or drug
3. Received prior radiation therapy or chemotherapy for glioblastoma
4. History of allergic reaction/hypersensitivity to DSF (without alcohol) or copper.
5. Treatment with the following medications that may interfere with metabolism of DSF: warfarin (unless otherwise chosen by the study PI who will actively adjust Coumadin dose to consistently maintain a safe, therapeutic INR < 3), theophylline, amitriptyline, isoniazid, metronidazole, phenytoin, phenobarbital, chlorzoxazone, halothane, imipramine, chlordiazepoxide, diazepam. (Note: lorazepam and oxazepam are not affected by the P450 system and are not contraindicated with DSF).
6. Active severe hepatic or renal disease
7. Grade 2 or higher peripheral neuropathy or ataxia per NCI CTCAE version 4.0 (2009)
8. History of idiopathic seizure disorder schizophrenia, or psychosis unrelated to glioblastoma, corticosteroid, or anti-epileptic medications
9. History of Wilson's or Gilbert's disease
10. Current excessive use of alcohol.

3.3 Inclusion of Women and Minorities

Both men and women and members of all races and ethnic groups are eligible for this trial.

4.0 TREATMENT PLAN

This study is a single arm, open-label, phase II study of DSF-Cu in combination with concurrent temozolomide and radiation therapy followed by DSF – Cu and adjuvant temozolomide for patients with unmethylated tumors.

4.1 Pretreatment Evaluation

Prior to enrollment, patient must have a complete history, physical examination including neurological exam, evaluation of performance status using the ECOG, assessment of corticosteroid usage (mg per day), baseline laboratory studies (CBC, CMP, and Cu) and pregnancy test (if applicable), and brain MRI. A baseline MRI must be performed prior to registration.

Adjuvant temozolomide should be taken at bedtime on an empty stomach and should not be taken within one hour of DSF-Cu administration. Patients will be instructed to fast at least 2 hours before and 1 hour after temozolomide administration. Water is allowed during the fast period. If vomiting occurs during the course of treatment, no re-dosing of the patient is allowed before the next scheduled dose.

Patients will be instructed to bring their completed medication diary (Appendix C) to the study visit for assessment of compliance.

If patients receive the IV formulation of Temozolomide, compliance will be assessed by review of the medical record daily administration.

4.3 Study Evaluations

Consistent with standard of care, patients will be seen approximately every 4 weeks. At each visit, a ECOG evaluation and corticosteroid usage (mg per day) will be recorded. Brain MRI will be obtained every 8 weeks to assess for radiological response. Quality of Life (QOL) will be assessed using the Edmonton Symptom Assessment System – Revised (ESAS-r) questionnaire. Subjects will be monitored for copper levels on Day 1 (+/- 7 days) of Cycle 1 and Cycle 4 of adjuvant temozolomide.

Patients are evaluated for adverse events for 30 days from the last treatment of DSF-Cu, or until death, whichever occurs first. Patients removed from study for unacceptable adverse events will be followed until resolution or stabilization of the adverse event. Patients will also be removed from the study for non-compliance.

Table 2: Potential Adverse Events Related to DSF

MedDRA Term	Frequency: Likely: greater than 10% Less Likely: 1-10% Rare: 1% or less
Neoplasms	Rare: Tumor necrosis
Blood and lymphatic system disorders	Rare: Neutropenia, anemia, leukopenia, thrombocytopenia, lymphopenia (likely due to temozolomide)
Immune system disorders	Rare: Hypersensitivity
Metabolism and nutrition disorders	Likely: Alcohol intolerance, metallic or garlic-like aftertaste
Psychiatric disorders	Less Likely: psychosis, delirium (need to rule out tumor progression)
Nervous system disorders	Likely: Drowsiness, headache, confusion Less Likely: ataxia, gait disturbance, peripheral neuropathy Rare: Extrapyrarnidal symptoms
Eye disorders	Rare: Optic neuritis
Cardiac disorders	Less Likely: Tachycardia, hypotension (need to rule out DSF-alcohol reaction)
Respiratory, thoracic, and mediastinal disorders	Less Likely: Dyspnea (need to rule out DSF-alcohol reaction)
Gastrointestinal disorders	Likely: Nausea, vomiting, diarrhea Less Likely: constipation (likely due to temozolomide)
Hepatobiliary disorders	Rare: Hepatitis
Skin and subcutaneous tissue disorders	Less Likely: Allergic dermatitis
Musculoskeletal	Rare: Arthralgia, myalgia
Renal and urinary disorders	Rare: Dysuria, hematuria
Reproductive system	Less likely: impotence
General disorders	Likely: Fatigue

4.4 General Concomitant Medication/Treatment and Supportive Care Guidelines

Treatment with Optune[®] may be initiated by Day 1 of Cycle 1, but can begin at any time prior to this as long as it is not started until after completion of radiation therapy. If patient did not declare intent for Optune[®] to start on Day 1 of Cycle 1, treatment with Optune[®] may be initiated on Day 1 of Cycle 6, otherwise it may not be initiated until all protocol therapy is completed.

The following medications and procedures are prohibited during the study:

- Any antineoplastic therapy (other than those already used for the treatment of autoimmune disorders) other than temozolomide and DSF
- Any investigational therapy other than DSF or Cu

All other medical conditions or manifestations of the patient's malignancy should be treated at the discretion of the investigator in accordance with local community standards of medical care.

Patients should not drive, operate dangerous tools or machinery, or engage in any other potentially hazardous activity that requires full alertness and coordination if they experience sedation while enrolled in this study.

Patients are to be instructed to abstain from alcohol while enrolled in this study.

